15.3.2. Handling of missing data for Patient-Reported Outcomes (PROS)

Patient-Oriented Eczema Measure (POEM)

- If only one question is left unanswered, this is scored 0 and the scores are summed and expressed as usual out of a maximum of 28
- If more than one question is left unanswered, the questionnaire is not scored
- If 2 or more response options are selected for a single question, the response option with the highest score will be recorded.

PROMIS Sleep Related Impairment SF8a Total Score

The total score for PROMIS is the sum of 8 item scores.

- For any missing item score at a specific time point, the mean of the remaining non-missing item scores for that patient at this specific time point is used to impute the missing item score(s). In these cases, the total score is calculated as the sum of the observed and the imputed item scores

Dermatology Life Quality index (DLQI)

- If only one question is left unanswered, this is scored 0 and the scores are summed and expressed as usual out of a maximum of 30
- If 2 or more questions are left unanswered, the questionnaire is not scored
- If 2 or more response options are selected for a single question, the response option with the highest score should be recorded
- Related to question 7:
 - If question 7 is answered “yes”, this is scored 3
 - If question 7 is answered “no” but then either “a lot” or “a little” is ticked, this is then scored 2 or 1 (respectively).
 - If “not relevant” is ticked, this is scored 0
 - If question 7 is answered “no”, but the second half is left incomplete, the score will remain 0.

Juniper Asthma Control Questionnaire (ACQ-5)

- If only one question is left unanswered at a specific time point,
 - If the questionnaire from the previous time point is complete, it is interpolated (pro-rated) using the completed questions from the previous time point
 - If the questionnaire from the previous time point is not complete, the missing value will be imputed as the average of the completed questions within the current visit.
- If 2 or more questions are left unanswered, the global score is invalid and is considered as missing

Hospital Anxiety and Depression Scale (HADS)

- If only one question is left unanswered in the Anxiety subscale (sum of all the A questions) or Depression subscale (sum of all D questions) at a specific time point, a score can be computed using the person specific mean of the corresponding subscale at this specific time point
- If 2 or more questions are left unanswered in the Anxiety subscale or Depression subscale, the score is invalid and is considered as missing in the corresponding subscale.

Other Patient-Reported Outcomes

For all other questionnaires, if one or more questions are left unanswered, the questionnaire is not scored.

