15.8. Patient-Reported Outcomes (PROS)

Patient oriented eczema measure (POEM)

The POEM is a 7-item, validated questionnaire used in clinical practice and clinical trials to assess frequency of disease symptoms in children and adults (9). The format is a response to 7 items (dryness, itching, flaking, cracking, sleep loss, bleeding, and weeping) based on frequency during the past week (ie, 0 = no days, 1 = 1 to 2 days, 2 = 3 to 4 days, 3 = 5 to 6 days, and 4 = all days) with a scoring system of 0 to 28; the total score reflects disease-related severity.

POEM score will be directly provided by KONEKSA.

PROMIS Sleep Related Impairment Short Form 8a

The PROMIS is a DSM-5, Level 2, sleep disturbance measure. This study uses the 8-item PROMIS Sleep Related Impairment Short Form that assesses the domain of sleep related impairment in the past 7 days in individuals age 18 and older.

Each item asks the patient to rate the severity of the patient’s sleep related impairment during the past 7 days. Each item on the measure is rated on a 5-point scale (1 = not at all; 2 = a little bit; 3 = somewhat; 4 = quite a bit; and 5 = very much) with a range in score from 8 to 40 with higher scores indicating greater severity of sleep impairment.

Locate the applicable score conversion in [Table 15.8.1](#), and use this table to translate the total raw score or imputed total score into a PROMIS T-score for each participant. The T-score rescales the raw score into a standardized score with a mean of 50 and a standard deviation of 10. Therefore, a person with a T-score of 40 is one SD below the mean. The standardized T-score is reported as the final score for each participant.

Table 15.8.1 PROMIS Sleep-Related Impairment conversion table

Raw Score	T-score	Raw Score	T-score
8	30	25	60.3
9	35.1	26	61.3
10	38.7	27	62.3
11	41.4	28	63.3
12	43.6	29	64.3
13	45.5	30	65.3
14	47.3	31	66.3
15	48.9	32	67.3
16	50.3	33	68.4
17	51.6	34	68.5
18	52.9	35	70.7
19	54	36	71.9
20	55.1	37	73.3
21	56.1	38	75
22	57.2	39	76.9
23	58.2	40	80
24	59.3		

PROMIS score will be directly provided by KONEKSA.

Epworth Sleepiness Scale (ESS)

The ESS is a self-administered questionnaire with 8 questions. Respondents are asked to rate, on a 4-point scale (0-3), their usual chances of dozing off or falling asleep while engaged in eight different activities. Most people engage in those activities at least occasionally, although not necessarily every

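### SAP 15.3.2 scores PROMIS (key secondary 4) from any number of answered items, and fractional pro-rated totals have no row in the T-score table

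*SAP*

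**What the plan says.** **Scoring and missing items (SAP 15.3.2).** "The total score for PROMIS is the sum of 8 item scores". For incomplete forms the rule begins "For any missing item score at a specific time point, the mean of the remaining non-missing item scores for that patient" and applies that mean to the missing item or items; then "the total score is calculated as the sum of the observed and the imputed item scores". No minimum number of answered items is given, and no rounding.

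**Other instruments in the same section.** POEM, DLQI, ACQ-5 and each HADS subscale may have one item missing and are not scored once two are. Any questionnaire not named there is not scored if a single item is missing.

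**Conversion (SAP 15.8).** "Each item on the measure is rated on a 5-point scale", "with a range in score from 8 to 40". The analyst is told to "use this table to translate the total raw score or imputed total score into a PROMIS T-score for each participant". Table 15.8.1 lists whole raw scores only. "The standardized T-score is reported as the final score for each participant". The same section says that the vendor supplies the PROMIS score.

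**Use.** SAP 8.2.10 models change from baseline in both the raw score and the T-score with the primary MMRM. SAP 8.2.23 places PROMIS fourth among the key secondary endpoints, ahead of the four actigraphy endpoints, without saying which of the two scores is tested.

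**The concern.** There are two separate gaps.

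First, a form with one answer is scaled up to an eight-item total and enters the MMRM with the same weight as a complete form. PROMIS is the only multi-item patient questionnaire in the testing hierarchy, yet it is the only one in SAP 15.3.2 without a limit on missing items. No reason for the difference is given.

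Second, the SAP sends imputed totals to a table that cannot always take them. With one item missing, most possible totals fall between two rows, and the programmer must choose whether to round, truncate or interpolate.

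At stake is the precision and reproducibility of an endpoint that must succeed before the actigraphy endpoints can be declared significant.

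**Working it through.** **The plan's own range.** Eight items scored 1 to 5 give 8 × 1 = 8 and 8 × 5 = 40. This reproduces the stated range and the 33 whole-number rows of Table 15.8.1.

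**Pro-rated total.** With k items answered and sum S (from k to 5k), replacing each missing item by S/k gives S + (8 − k) × S/k = 8S/k. Listing every possible total:

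| Items answered, k | Possible totals | Totals with no table row |
|---|---|---|
| 1 | 5 | 0 |
| 2 | 9 | 0 |
| 3 | 13 | 8 |
| 4 | 17 | 0 |
| 5 | 21 | 16 |
| 6 | 25 | 16 |
| 7 | 29 | 24 |
| 8 | 33 | 0 |

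For seven items this is 24/29 = 83% of possible totals. It is a share of possible values, not of forms. The two gaps affect different forms: one, two or four answers always give a whole number.

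**Effect on one T-score.** Seven items summing to 20 give 8 × 20/7 = 22.86. The rows are 57.2 (raw 22) and 58.2 (raw 23). Truncating gives 57.2, rounding to nearest gives 58.2, and interpolating gives 57.2 + 0.86 × 1.0 = 58.1.

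The smallest incomplete total above 8 is 8 + 8/7 = 9.14, so the widest step in the table (5.1, between raw 8 and 9) is never in question. By the same argument the largest total below 40 is 40 − 8/7 = 38.86. The widest step that can matter is 38.7 − 35.1 = 3.6 (raw 9 to 10); between raw 18 and 33 the steps are 1.0 to 1.1. The smallest step, 0.1 between raw 33 (68.4) and raw 34 (68.5), is followed by 2.2 to raw 35 (70.7). That row is worth checking against the source table.

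**Effect of a single answer.** The only possible totals are 8, 16, 24, 32 and 40, with T-scores 30, 50.3, 59.3, 67.3 and 80. Moving that one answer from 3 to 4 moves the total by 8 raw points and the T-score by 67.3 − 59.3 = 8.0.

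**Error of a pro-rated total.** The documents give no item-level data. Assume item SD 1, equal inter-item correlation r between 0.5 and 0.7, and items missing without regard to content. Then:

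- error SD = 8 × √[(1 − r)(1/k − 1/8)]
- SD of the complete total = √(8 + 56r)

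| r | k = 1 | k = 4 | k = 7 | Total-score SD |
|---|---|---|---|---|
| 0.5 | 5.3 | 2.0 | 0.8 | 6.0 |
| 0.6 | 4.7 | 1.8 | 0.7 | 6.5 |
| 0.7 | 4.1 | 1.5 | 0.6 | 6.9 |

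From one item the error SD is 88% (5.29/6.0) down to 60% (4.10/6.87) of the total-score SD. From seven items it is at most 13% (0.76/6.0).

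**The case against.** The practical effect may be close to nil. SAP 8.1.7 describes patient questionnaires completed on an iPad, so incomplete forms should be few. The likeliest incomplete form lacks one item, and pro-rating that is accurate. Missing-item rules may properly differ between instruments, and the SAP history shows that the PROMIS rule was revised for version 2.0. The vendor supplies the score and may already have a rule. A competent programmer would round sensibly.

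Much of this stands, and it keeps the point small. But neither document says that items are mandatory on screen, and SAP 15.3.2 itself plans for unanswered ones. No vendor rule for incomplete forms is documented, and the revised text still has no minimum.

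Three stronger readings are tempting, and the documents do not support them:

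- **Near-empty forms are the ones with no T-score.** They are not: one, two or four answers always land on a table row.
- **The raw-score and T-score analyses would use different patients.** Nothing in the SAP sets an unmatched T-score to missing. Sending imputed totals to the table shows that a T-score is intended for them; what is missing is the rounding convention.
- **The table gap compromises the gate to the actigraphy endpoints.** Protocol Table 1 and SAP Table 3.1.1 define the endpoint on the total score, and the raw-score MMRM accepts fractional totals. The gate could be touched only if the T-score is confirmatory, which SAP 8.2.23 leaves open.

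**Conclusion.** Both gaps are real and minor. The missing minimum is the more substantive, because a stated limit is a better method than the one written. The table gap is an unstated convention that affects the T-score alone.

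The per-form error sizes rest on the assumed item SD, correlation and missingness above. They do not translate into an effect on the treatment difference, power or type I error, because the number of incomplete forms is not given. If it is small, as electronic entry suggests, the effect on the comparison is likely minor. This is a cheap improvement to make before unblinding, not a threat to the trial's conclusions.

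**What to change.** 1. In SAP 15.3.2, score PROMIS only when a stated minimum number of items is answered, and otherwise set it to missing. At least half (4 of 8) keeps more forms, with an error SD of about 2.0 to 1.5 raw points under the assumptions above. Requiring 7 of 8 matches the sibling scales. Neither threshold is given for PROMIS in the documents, so the choice is a judgement; what matters is that one is stated.
2. In SAP 15.8, round the pro-rated total to the nearest whole number before the look-up. This is needed even with a 7-of-8 limit. It is never ambiguous: a total ending in exactly .5 would require 16S = k × (an odd number), which is impossible for k from 1 to 8.
3. In SAP 8.2.23, say whether the raw score or the T-score is confirmatory.
4. Confirm that the vendor applies the same rules.

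The cost is a few lines of SAP text and one scoring check. The downside is that a few near-empty forms become missing; the MMRM already handles missing values without imputation.

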15.3.3. Handling of missing data for Clinician Reported Outcomes (CLINROS)

No imputation will be made for missing or incomplete data.

15.4. Missing Safety Data

For categorical variables, patients with missing data are not included in calculations of percentages unless otherwise specified. When relevant, the number of patients with missing data is presented.

15.4.1. Handling of missing age

If age is missing but year of birth is collected, then age will be derived as date of informed consent signed minus year of birth and June 30th, keeping the integer part of the result.

15.4.2. Handling of computation of treatment duration if investigational medicinal product end of treatment date is missing

For the calculation of the treatment duration, the date of the last dose of IMP is equal to the date of last administration reported on the e-CRF “Treatment status” page. If this date is missing, the last available administration date in the “Exposure” form will be used.

The last dose intake should be clearly identified in the eCRF and should not be approximated by the last returned package date

15.4.3. Handling of medication missing/partial dates

No imputation of medication start/end dates or times will be performed. If a medication date or time is missing or partially missing and it cannot be determined whether it was taken prior or concomitantly, it will be considered a prior, concomitant and post-treatment medication.

15.4.4. Handling of adverse events with missing or partial date/time of onset

Missing or partial adverse event onset dates and times will be imputed so that if the partial adverse event onset date/time information does not indicate that the adverse event started prior to treatment or after the treatment-emergent adverse event period, the adverse event will be classified as treatment-emergent. No imputation of adverse event end dates/times will be performed. These data imputations are for categorization purpose only and will not be used in listings. No imputation is planned for date/time of adverse event resolution.

15.4.5. Handling of adverse events when date and time of first investigational medicinal product administration is missing

When the date and time of the first IMP administration is missing, all adverse events that occurred on or after the day of randomization should be considered as treatment-emergent adverse events. The exposure duration should be kept as missing.

The last dose intake should be clearly identified in the eCRF and should not be approximated by the last returned package date.

15.4.6. Handling of missing assessment of relationship of adverse events to investigational medicinal product

If the assessment of the relationship to IMP is missing, then the relationship to IMP has to be assumed and the adverse event considered as such in the frequency tables of possibly related adverse events, but no imputation should be done at the data level.

15.4.7. Handling of missing severity/grades of adverse events

If the severity/grade is missing for 1 of the treatment-emergent occurrences of an adverse event, the maximal severity on the remaining occurrences will be considered. If the severity is missing for all the occurrences, a “missing” category will be added in the summary table.

15.4.8. Handling of potentially clinically significant abnormalities

If a patient has a missing baseline he will be grouped in the category “normal/missing at baseline.”

For PCSAs with 2 conditions, one based on a change from baseline value or a normal range and the other on a threshold value, with the first condition being missing, the PCSA will be based only on the second condition.

15.5. Visit Windows

The following steps will decide how the scheduled and/or unscheduled visits will be used in the analyses on efficacy variables and the by-visit summaries for safety variables.

Step 1: A scheduled measurement (described in [Appendix 15.2](#)) will be used if it is available; otherwise, an unscheduled measurement (including the end of treatment/study visit for those prematurely discontinued) will be used if it happens to be on the same date as the date of the scheduled visit.

Step 2: After Step 1, if there is still no measurement for a given parameter at a scheduled visit, the analysis window below “[in brackets]” will be applied to re-allocate a post-baseline unscheduled measurement to a scheduled measurement.

Table 15.5.1 Analyses window definition

Scheduled visit post baseline	Targeted study day	Analysis window			
		PSG	Weight	PVT, ANAM, ACQ-5 and AR-VAS	All other endpoints/parameters
Week 1 (Visit 2)	7				[1, 11]
Week 2 (Visit 3)	14				[12, 21]
Week 4 (Visit 4)	28				[22, 42]
Week 8 (Visit 5)	56				[43, 70]
Week 12 (Visit 6)	84	[1,~]		[1, 126]	>=71 for patients who did not enter OLE. [71, 1st dose date of OLE[for patients entered OLE.
Week 16 (Visit 7)	112				[First dose of OLE, 126]
Week 20 (Visit 8)	140				[127, 154]

Scheduled visit post baseline	Targeted study day	Analysis window		
		PSG	Weight	PVT, ANAM, ACQ-5 and AR-VAS
Week 24 (Visit 9)	168		[1,~]	[127,~]
				All other endpoints/parameters [155, ~]

Study days are calculated from the day of first administration of IMP; the day of first administration of IMP (or the day of randomization if not exposed) is Day 1.

For endpoints with daily assessments until Week 4, Week 3 will be summarized. Week 3 visit is assigned to records which lie on the 7 days following the final day of Week 2. If this 7 day window overlaps with already assigned Week 4 records then Week 3 will have a duration of less than 7 days.

After applying the above time windows, if multiple assessments are associated to the same time point, the closest from the targeted study day will be used. In case of equality, the last measurement will be used. Re-allocated scheduled visits (i.e., visit numbers) should be sequential if ordered by the date of measurement.

After Step 2, if there is still no measurement for a given parameter at a scheduled visit, data is considered missing.

For endpoints where measurements were only scheduled once for post-baseline (e.g., weight at week 24 and PSG at week 12), the measurement that is closest to the target day will be used.

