3.1. Overall Study Design and Plan

This is a Phase IV, prospective, 2:1 randomized, multinational, multicenter study, with a 12-week double-blind placebo-controlled period, followed by a 12-week open label extension to evaluate the effect of dupilumab on sleep in adult patients with moderate to severe AD.

[figure not shown]
Approximately 201 participants will be randomly assigned to study intervention in a 2:1 dupilumab to placebo ratio from multiple sites globally such that at least 150 evaluable participants (100 in the active group and 50 in placebo) complete the double-blind portion (to week 12) of the study.

The study will comprise of:

- Screening Period 1 (Day -28 to -8): Patients will be evaluated according to inclusion and exclusion criteria
- Screening Period 2 (Day -7 to -1; pre-baseline assessments): eligible patients will complete the daily sleep quality, daily pruritus, skin pain, skin sensitivity, and touch skin burn, sleep diary, and will wear an actigraph at night-time during the 7 days immediately preceding the Baseline visit (Day 1). If preferred by the patient and the investigator for logistical reasons, screening can be done during a single on-site visit. In that case, all procedures planned at screening 1 and screening 2 should be done during this single screening visit. Importantly, this single screening visit will have to be done at least 7 days before the baseline visit, as patients should wear the actigraph and complete the diary for 7 days before baseline.
- Baseline (Day 1): Patients who remain eligible will be randomized
- 12-week double-blind placebo-controlled period: Patients will be randomized to receive dupilumab or placebo
- 12-week open-label extension period: following completion of double-blind period, patients randomized to dupilumab will continue to receive active treatment for open-label period, whereas patients randomized to placebo will receive active treatment with dupilumab.

The maximum study duration per participant will be 28 weeks. A patient is considered to have complete the study if he/she has completed all phases of the study including the last scheduled visit shown in the Schedules of Activities (see [Appendix 15.2](#)).

Figure 3-1 Study Plan

Abbreviations: q2w=every 2 weeks

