4.4.3. Visit Windows

The visit windows as defined in [Section 15.5](#) will be applied to all endpoints.

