4.4.4. Unscheduled Visits

Unscheduled visit measurements will be used in the analysis on efficacy variables and will be included in the by-visit summaries for the safety variables if they are re-allocated to scheduled visits according to the visit window definitions in [Section 15.5](#).

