For the analysis of primary objective in the double-blind treatment period,

- The null statistical hypothesis tested is that there is no treatment difference between dupilumab and placebo on sleep quality NRS in adult patients with moderate to severe AD and sleep disturbance.
- the alternative statistical hypothesis tested is that there is a treatment difference between dupilumab and placebo on sleep quality NRS in adult patients with moderate to severe AD and sleep disturbance.

Note that due to the small sample size in the PSG analysis set, no statistical testing will be conducted for PSG related endpoints. Summary statistics with 95% CI by treatment group will be provided.

Statistical testing will be only be conducted on results for the double-blind treatment period. Statistical testing will not be conducted for the assessments completed during OLE period. All related endpoints will be summarized.

All efficacy measurements collected during the study will be considered for analyses, including those obtained after IMP discontinuation.

All daily assessments (e.g., sleep quality NRS, actigraphy parameters, sleep diary, etc.) will be analyzed as weekly averages for the week immediately preceding the study visit.

Line plots for change from baseline or percent change from baseline will be presented by treatment group, displaying the mean, median, Q1 and Q3 at each visit. These plots will be provided for the primary and all secondary continuous endpoints.

Bar plots for percentage of patients with EASI50, EASI75 and EASI90 will be presented by treatment group, displaying the percentage of EASI responders at each visit.

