15.2. Schedule of Study Procedures

Study Procedure													
Visit (V)	Screening 1 ^g	Screening 2 ^g	Baseline V1	V2	V3	V4	V5	Primary End point Visit V6	V7	V8	End of Study/ Early discontinuation V9 ^h	UnSch Visit	Notes
Week (W)			W0	W1	W2	W4	W8	W12	W16	W20	W24		
Day (D)				D8	D15	D29	D57	D85	D113	D141	D169		
Visit window (±d)	D (-28 to -8)	D (-7 to -1)	D1	±3d	±3d	±3d	±3d	±3d	±3d	±3d	±3d		
Enrollment Screening/Baseline:													
Inclusion and exclusion criteria	X		X										
Informed consent	X												
Demography	X												
Concurrent illness	X		X										
IVRS call	X		X		X	X	X	X	X	X	X		
Study Treatment/Concomitant Medication:													
Study drug dispensation			X ^a		X ^b	X	X	X ^c	X	X			
Concomitant medications and procedures	X	X	X	X	X	X	X	X	X	X	X	X	
Efficacy:													
Physician Assessments:													

Study Procedure													
Visit (V)	Screening 1 ^g	Screening 2 ^g	Baseline V1	V2	V3	V4	V5	Primary End point Visit V6	V7	V8	End of Study/ Early discontinuation V9 ^h	UnSch Visit	Notes
Week (W)			W0	W1	W2	W4	W8	W12	W16	W20	W24		
Day (D)			D1	D8 ±3d	D15 ±3d	D29 ±3d	D57 ±3d	D85 ±3d	D113 ±3d	D141 ±3d	D169 ±3d		
Visit window (±d)	D (-28 to -8)	D (-7 to -1)											
IGA and BSA (for eligibility purpose only)	X		X										
EASI	X		X	X	X	X	X	X	X	X	X	X	
SCORAD	X		X	X	X	X	X	X	X	X	X	X	
Patient Assessments (Daily including week preceding baseline visit):													
Sleep Quality NRS ^d		X	X	X	X	X	X	X	X	X	X	X	
Sleep Diary ^d		X	X	X	X	X	X	X	X	X	X	X	
Peak pruritus NRS, Skin pain NRS, Skin sensitivity to touch, Skin burn NRS ^d		X	X	X	X	X	X	X	X	X	X	X	
Actigraphy ^d		X	X	X	X	X	X	X	X	X	X	X	
Patient Assessment (at clinic):													
PROMIS Sleep Related Impairment SF 8a			X	X	X	X	X	X	X	X	X	X	
Epworth Sleepiness Scale (ESS)			X			X		X			X	X	

Study Procedure													
Visit (V)	Screening 1 ^g	Screening 2 ^g	Baseline V1	V2	V3	V4	V5	Primary End point Visit V6	V7	V8	End of Study/ Early discontinuation v9 ^h	UnSch Visit	Notes
Week (W)			W0	W1	W2	W4	W8	W12	W16	W20	W24		
Day (D)			D1	D8	D15	D29	D57	D85	D113	D141	D169		
Visit window (±d)	D (-28 to -8)	D (-7 to -1)	D1	±3d	±3d	±3d	±3d	±3d	±3d	±3d	±3d		
POEM			X			X		X			X	X	
DLQI			X			X		X			X	X	
HADS			X			X		X			X	X	
ACQ-5, AR-VAS			X					X			X	X	
WPAI-AD			X			X	X	X			X	X	
Assess missed school/work days			X			X	X	X	X	X	X	X	
Center assisted Assessment:													
Psychomotor Vigilance Test (PVT)	X		X					X			X	X	

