d For patients who do not participate to the PSG sub-study: Patients eligible to continue, except for baseline severity criteria, will complete baseline assessments from Day -7 to Day -1 (right before Day 1); daily assessment thereafter until week 4; then only the week before a clinical visit until last study visit. For patients who participate to the PSG sub-study: same procedures as for the other patients, except that the sleep quality NRS and the peak pruritus NRS will be completed for 5 days, from Day -7 to Day -3 prior to baseline.

- e Each patient who participates in this sub-study will have a total of 3 overnight PSGs: at baseline time point, 2 (preferably) consecutive overnight PSGs to control for "first night effect" and collect baseline data, and 1 more at week 12.
- f Not mandatory, site professional will be taking the photographs with patient's consent; Site staff will take the photos of the same lesioned areas for each visit, starting from the baseline visit. Patients will be asked to sign a separate photography informed consent at Day 1.
- g If preferred by the patient and the investigator for logistical reasons, screening can be done during a single on-site visit. In that case, all procedures planned at screening 1 and screening 2 should be done during this single screening visit. Importantly, this single screening visit will have to be done at least 7 days before the baseline visit, as patients should wear the actigraph and complete the diary for 7 days before baseline.
- h V9 assessments are applied to patients who prematurely discontinue the study, complete the treatment (end of treatment), and complete the study (end of study).

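### SAP Table 15.5.1: the Week 12 window for PVT, ANAM, ACQ-5 and AR-VAS runs to Day 126 and is not cut at the first open-label dose

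*SAP*

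**What the plan says.** SAP 4.4.3 states that the visit windows of section 15.5 "will be applied to all endpoints". SAP 4.4.4 adds: "Unscheduled visit measurements will be used in the analysis on efficacy variables", provided the windows re-allocate them to a scheduled visit.

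SAP 15.5 works in two steps. Step 1 takes the scheduled measurement. Failing that, it takes "an unscheduled measurement (including the end of treatment/study visit for those prematurely discontinued") if it falls on the scheduled date. If the visit is still empty, Step 2 applies the Table 15.5.1 window, which "will be applied to re-allocate a post-baseline unscheduled measurement to a scheduled measurement".

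The Week 12 row of that table reads:

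| Column | Week 12 window |
|---|---|
| PSG | [1,~] |
| PVT, ANAM, ACQ-5 and AR-VAS | [1, 126] |
| All other endpoints, OLE not entered | Day 71 onward |
| All other endpoints, OLE entered | Day 71 up to, but not including, the first OLE dose date |

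The schedule in SAP 15.2 marks all four assessments at Week 12, at V9 and at unscheduled visits. Its footnote h says "V9 assessments are applied to patients who prematurely discontinue the study". SAP 8.2.14 to 8.2.17 compare the arms at Week 12 on these assessments by MMRM, with a confidence interval and p-value. SAP section 8 says: "Statistical testing will not be conducted for the assessments completed during OLE period".

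**The concern.** Placebo patients who enter the OLE receive dupilumab from Week 12 (SAP 3.3). Suppose one of them misses the Week 12 PVT, starts open-label dosing and leaves the study at Day 110. The V9 PVT counts as unscheduled, falls inside [1, 126] and is labelled Week 12. The patient is then analysed as placebo on a value measured on dupilumab. In the column for all other endpoints, the same record would go to Week 16.

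Such values tend to shrink the Week 12 difference. Late dupilumab-arm values relabelled in the same way could partly offset this if those patients had improved further, or add to it if they left while worsening. The net size is therefore uncertain.

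**Working it through.** **Where Day 126 comes from.** The table's limits are midpoints between consecutive target days.

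- General column (targets 7, 14, 28, 56, 84, 112, 140, 168): the midpoints are 10.5, 21, 42, 70, 98, 126 and 154. The printed upper limits are 11, 21, 42, 70, the first OLE dose, 126 and 154. Only the Week 12/Week 16 limit departs from the rule: Day 98 gives way to the first OLE dose date.
- PVT/ANAM/ACQ-5/AR-VAS column (targets 84 and 168): (84 + 168)/2 = 126, as printed. Here the midpoint rule was left in place.

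**Open-label time inside the window.** The schedule puts Week 12 at Day 85 ±3.

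- First OLE dose on Day 85: 126 − 85 = 41 days. On Day 88: 126 − 88 = 38. On Day 82: 126 − 82 = 44.
- Two-weekly dosing from Day 85 gives doses on Days 85, 99 and 113, with the next on Day 127. The window therefore covers three open-label dosing occasions on the nominal schedule.

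**Weight of an affected placebo patient.** Week 12 is the only post-baseline visit in the double-blind period for these assessments, so no earlier visit dilutes the effect. Approximately:

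shrinkage = k × s / n

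Here k is the number of affected placebo patients (assumed) and s is the share of the full drug effect present in their values (assumed). For n there are two values: 67 randomised (201/3), or 50 from the SAP 3.1 target of "at least 150 evaluable participants (100 in the active group and 50 in placebo) complete the double-blind portion".

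| k | s | n = 67 | n = 50 |
|---|---|---|---|
| 1 | 1 | 1.5% | 2.0% |
| 1 | 0.5 | 0.7% | 1.0% |
| 3 | 1 | 4.5% | 6.0% |
| 5 | 1 | 7.5% | 10.0% |

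**Both arms affected.** If the same share r of each arm is relabelled, and the dupilumab-arm values move by a fraction g of the effect (positive means further improvement), net shrinkage = r × (s − g). At r = 2%:

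| s | g = 0.25 | g = 0 | g = −0.25 |
|---|---|---|---|
| 1 | 1.5% | 2.0% | 2.5% |
| 0.5 | 0.5% | 1.0% | 1.5% |

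r and g are assumptions.

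**Subset endpoints.** ACQ-5 and AR-VAS are analysed only in patients with asthma or allergic rhinitis at baseline. Those numbers are not given. If 17 to 25 of 50 placebo patients qualify (assumption), one affected patient weighs 1/25 = 4.0% to 1/17 = 5.9% at s = 1.

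**The case against.** The strongest reply is that SAP section 8 already bars testing of assessments done in the OLE period, and that it governs which records are tested while Table 15.5.1 only assigns labels. SAP section 12 points the same way: comparative efficacy is analysed after the lock of the double-blind portion. This shows the intent, but no derivation rule carries it out. Section 8 also says that all efficacy measurements collected will be considered. Section 12 sets no record-level cutoff. OLE entry is not an intercurrent event in SAP 4.5, and SAP 15.3.1 does not set post-OLE values to missing. A programmer following the table would include the value.

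SAP 15.5 also asks that re-allocated visits be sequential by date. This does not block the relabelling, because the next visit for these four assessments is Week 24.

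The argument about reach does stand. The patient must receive the open-label dose, lack a scheduled Week 12 test planned for the same visit, and then have an unscheduled or V9 test by Day 126. A late test recorded as the scheduled visit never reaches Step 2. For ACQ-5 and AR-VAS, where one patient would weigh most, SAP 8.1.7 expects patient-reported data to be complete because they can be entered at home. The counts of three and five patients show scale only; they are not forecasts.

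**Conclusion.** The window is wrong as written, at minor severity. One column of the Week 12 row protects the placebo-controlled comparison from open-label data and the other does not, which conflicts with section 8's restriction of testing to the double-blind period. That reading is firm.

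The size is not firm: the documents give no rate of affected patients, and k, s, r, g and the subset sizes are all assumed. A plausible effect is 1.5% to 2.0% of the treatment difference per affected placebo patient with full drug effect, about half that with half the effect, and more in the ACQ-5 and AR-VAS subsets. The four assessments are exploratory and outside the testing order in SAP 8.2.23. The primary and key secondary endpoints are not affected.

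**What to change.** In Table 15.5.1, split the Week 12 cell for PVT, ANAM, ACQ-5 and AR-VAS. For patients who entered the OLE, use [1, 1st dose date of OLE[, matching the neighbouring column. For patients who did not, keep [1, 126]. State that values from the first OLE dose to Day 126 in OLE entrants are listed but not assigned to Week 12.

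The cost is one cell edit, and a few late values become missing at Week 12 for four exploratory assessments. A scheduled Week 12 test done on the dosing day is kept, because Step 1 takes scheduled values first. The half-open bracket could drop a rare unscheduled test taken before dosing on the dose date; the general column already accepts that loss.

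The PSG cell [1,~] can take the same wording for consistency. It is not part of this point: no PSG test is planned, PSG is not scheduled at V9 or unscheduled visits, and a travel-delayed PSG moves together with Visit 6 (Protocol Appendix 10).
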